5.3 Baseline Patient Characteristics

Baseline characteristics will be compared across treatment groups. Table 1 in the MockTablesAppendix.docx document lists out maternal and neonatal characteristics that will be summarized in the primary published paper. In addition to the variables indicated in Table 1 of the MockTablesAppendix.docx document, other baseline characteristics may be investigated internally by the Premie Hypothermia Subcommittee. For programming purposes, the following list contains an example list of infant and maternal characteristics that will or may be investigated as well as dataset and variable names needed to locate the characteristics in the clinical database:

- Infant baseline characteristics (*Variable Type, Form, Variable name in clinical database*)
 - Birth year (*Multiple level discrete, PH05: A.1.a, PH5BRTDT*)
 - GA (*Multiple level discrete – at level of weeks, PH05: A.7.a, PH5GESTW*)
 - Sex (*Binary, PH05: A.8, PH5SEX*)
 - Birthweight (grams) (*Continuous, PH05: A.4, PH5BRTWT*)
 - Length (cm) (*Continuous, PH05: A.5, PH5BRTLN*)
 - Head circumference (cm) (*Continuous, PH05: A.6, PH5HCIRC*)
 - Seizures (*Binary, PH02: C.1, PH2SIEZ*)
 - Level of Encephalopathy (*Binary, PH02: G.4, PH2LECEP*)
 - Inborn/outborn status (*Binary, PH05: A.2, PH5OUTBN*)
 - 1-minute Apgar scores (*Continuous, PH05: A.3.a, PH5APG1*)

- 5-minute Apgar scores (*Continuous, PH05: A.3.b, PH5APG5*)
- Received resuscitation at delivery (*Binary, PH05: B.1-B.5, PH5OXYG / PH5BAGM / PH5CHCOM / PH5INTUB / PH5DRUGS. any equal to 'Y'*)
 - Types of resuscitation (*Multiple level discrete or individual binary, use PH05: B.1-B.5, PH5OXYG / PH5BAGM / PH5CHCOM / PH5INTUB / PH5DRUGS.*)
- Received resuscitation at 10 minutes (*Binary, PH05: C.1-C.5, PH5OXY10 / PH5BAG10 / PH5CHE10 / PH5INT10 / PH5DRG10. Any equal to 'Y'*)
 - Types of resuscitation (*Multiple level discrete or individual binary, use PH05: C.1-C.5, PH5OXY10 / PH5BAG10 / PH5CHE10 / PH5INT10 / PH5DRG10.*)

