³ The primary outcome calculation contains variables that are only available in the Premie Hypothermia Follow-up Database. When programming the primary outcome and other outcomes derived from the Premie Hypothermia Follow-up database, you may come across outcomes that are missing. If outcomes are missing, determine what variable in the derivation is causing the missingness and then review data, regarding the infant with a missing outcome, from the PF11, PF12, and PF09A forms. The PF11 form will tell you if particular data is available, and the PF12 form will have information about lost-to-follow-up and additional information that may help understand the condition of the infant. Review the data in these forms to better understand why the data is missing and document what you find in a text file.

⁴ In this SAP, FU refers to the Premie Hypothermia FU database.

- a Bayley III cognitive score between 70-84 (*FU.B3_COG70 = 0 and FU.B3_COG85 = 1*) and either
- a GMFCS level of 2 (*FU.GMF_LEV = 2*), or
- an active seizure disorder requiring ongoing anticonvulsant therapy and not attributable to another disease process (*PH02: C.1, PH2SIEZ = 'Y' or PF04 A.4 = 'Y'*), or
- a hearing deficit requiring amplification or cochlear implant to understand commands (*FU.HEARCOG = 1,2, or 3 or FU.HEARAID = 1, 2, or 3*).

Mild disability will be defined by:

- a cognitive score 70-84 (*FU.B3_COG70 = 0 and FU.B3_COG85 = 1*), or
- a cognitive score ≥ 85 (*FU.B3_COG70 = 0 and FU.B3_COG85 = 0*) and
- any of the following:
 - GMFCS level I (*FU.GMF_LEV = 1*),
 - seizure disorder (*PH02: C.1, PH2SIEZ = 'Y'*) or
 - hearing loss not requiring amplification (*FU:HEARIMP = 1 (B.2.b) and FU:HEARAID = 0 and FU:HEARCOG = 0 (B.2.b.2)*).

Normal will be defined by:

- a cognitive score ≥ 85 (*B3_COG70 = 0 and B3_COG85 = 0*) and
- the absence of any neurosensory deficits (*PH02 Q C.1. = 'N', FU.GMF_LEV = 0, FU.BLIND_06 = 0, FU.DEAF_06=0, FU.HEARAID=0, FU.HEARCOG = 0, FU.HEARIMP=0*)).

In addition to the above 4 levels of disability, a separate disability variable will be created to identify infants who have “Profound disability”. Profound disability will be indicated by the assignment of lowest possible Bayley score due to inability to test due to severity of impairment. Note: any infant with the profound disability variable equal to yes will also have the primary outcome variable equal to yes, since profound disability is a subclass of severe disability with respect to the primary outcome.

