6.4 Secondary Outcome

Table 3 of the MockTablesAppendix.docx document contains the secondary outcomes that will be summarized in the primary published paper. Secondary outcomes that may be considered during initial analysis will include but not necessarily limited to:

- death (*Binary, sources used to identify are listed in Section 6.1*)
- cause of death (withdrawal of support and reasons for such will be tracked) (*Multiple level discrete, PH13 PH13DCOD.*)
- disability in survivors (*Multi-level discrete, None/mild/moderate/Severe disability, derivations given in Section 6.1*)
- death or profound disability (assignment of lowest score on Bayley III because untestable due to degree of impairment) (*Binary, sources used to identify death are listed in Section 6.1, will need to use NF9a.nf9acsur variables to identify infants who had Bayley III cognitive score set to lowest score due to severe delay in development.*)
- survival with no disability (*Binary, no indication of death and disability assessment equal 'Normal' as calculated in Section 6.1*)
- death or severe disability (*Binary, indication of death and indication of severe disability assessment as calculated in Section 6.1*)
- moderate or severe disability among survivors (*Binary, use information regarding death and section 6.1 for calculation*)
- severe disability among survivors (*Binary, use information regarding death and section 6.1 for calculation*)
- moderate disability among survivors (*Binary, use information regarding death and section 6.1 for calculation*)
- profound disability among survivors (*Binary, use information regarding death and section 6.1 for calculation*)
- mild disability among survivors (*Binary, use information regarding death and section 6.1 for calculation*)
- no disability among survivors (*Binary, use information regarding death and section 6.1 for calculation*)
- Cerebral palsy (Any, Quadriplegic, Diplegic, Hemiplegic, Dystonic, Athetotic, Ataxic, Other, Disabling (moderate or severe), (*Binary, using information from PF05 C.9.a, C.9.b, C.9.c.*)
- a Bayley III language score < 70 (*Binary, among survivors, see section 6.1*)
- a Bayley III language score 70 - 84 (*Binary, among survivors, see section 6.1*)
- a Bayley III language score >= 85 (*Binary, among survivors, see section 6.1*)
- a Bayley III motor score < 70 (*Binary, among survivors, see section 6.1*)
- a Bayley III motor score 70 - 84 (*Binary, among survivors, see section 6.1*)

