- a Bayley III motor score >= 85 (*Binary, among survivors, see section 6.1*)
- Head circumference < 10th percentile, among survivors (*Binary, based on PF05 follow-up form question A.3*)
- Weight < 10th percentile, among survivors (*Binary, based on PF05 follow-up form question A.1*)
- Length/height < 10th percentile, among survivors (*Binary, based on PH05 follow-up form questions*)
- each component of severe and moderate disability (among survivors):

- a Bayley III cognitive score < 70 (*Binary, see section 6.1*)
- a Bayley III cognitive score 70 - 84 (*Binary, see section 6.1*)
- a Bayley III cognitive score >= 85 (*Binary, see section 6.1*)
- Gross Motor Functional (GMFCS) Level of 3-5 (*Binary, see section 6.1*)
- blindness (visual acuity < 20/200 in the best eye as determined by an ophthalmologist) (*Binary, see section 6.1*)
- profound hearing loss (*Binary, see section 6.1*)
- a hearing deficit requiring amplification or cochlear implant to understand commands (*Binary, see section 6.1*)
- Seizures since discharge (*Binary, PF04 A.4 = 'Y'*)
- Abnormal neurological examination at discharge
- differences in MRI findings after cessation of cooling/control (*See subsection "Analysis of Ultrasound, CT scan, MRI and encephalopathy outcomes" under section 6.5.5 for more details*).

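### The Mild and Normal rules in SAP 6.1 take seizures only from the enrolment item, so a seizure disorder that appears after discharge cannot register in the Mild/Normal split

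*SAP*

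**What the plan says.** SAP 6.1 states that disability is determined by the network's standard interdisciplinary follow-up exam, then gives a rule with variable names for each level. Three of the rules involve seizures:

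- **Moderate** opens with "a Bayley III cognitive score between 70-84 (*FU.B3_COG70 = 0 and FU.B3_COG85 = 1*) and either" and lists an active seizure disorder among the qualifying conditions, coded as "PH2SIEZ = 'Y' or PF04 A.4 = 'Y".
- **Mild**, at a cognitive score of 85 or more, includes "seizure disorder (*PH02: C.1, PH2SIEZ = 'Y'*) or" as one qualifying limb. No follow-up seizure item is named.
- **Normal**, at 85 or more, requires no neurosensory deficit, coded as "PH02 Q C.1. = 'N', FU.GMF_LEV = 0, FU.BLIND_06 = 0, FU.DEAF_06=0, FU.HEARAID=0, FU.HEARCOG = 0" together with no hearing impairment. Its only seizure condition is the PH02 one.

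The SAP says elsewhere what the two items are. Section 5.3 lists "Seizures (*Binary, PH02: C.1, PH2SIEZ" among the infant baseline characteristics. Section 6.4 lists "Seizures since discharge (*Binary, PF04 A.4 = 'Y" as an outcome among survivors. Section 6.4 also defines survival with no disability as "no indication of death and disability assessment equal 'Normal' as calculated in Section 6.1".

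**The concern.** In words, a seizure disorder in a child scoring 85 or more is Mild disability. In code, the only seizure information used at that score is fixed before randomization. A seizure disorder that emerges after discharge therefore cannot move a child from Normal to Mild, although the item that would show it is collected and is already used in the Moderate rule.

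The outcomes at stake are those in section 6.4 that depend on the Mild/Normal boundary: survival with no disability, no disability among survivors, mild disability among survivors, and the four-level disability outcome. If the arms differ in later seizures, these outcomes cannot show it among children scoring 85 or more. The same child could be reported under seizures since discharge and also as having no disability.

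**Working it through.** **Step 1: apply the 6.1 rules as written.** Take a survivor with cognitive score 85 or more, GMFCS 0 and no vision or hearing deficit. Read Moderate plainly, as 70-84 AND (GMFCS 2 OR seizure disorder OR hearing deficit).

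| PH02 C.1 (enrolment) | PF04 A.4 (since discharge) | Class as written | Class with PF04 A.4 added to Mild and Normal |
|---|---|---|---|
| N | N | Normal | Normal |
| N | Y | **Normal** | **Mild** |
| Y | N | Mild | Mild |
| Y | Y | Mild | Mild |

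As written, PF04 A.4 never changes the class at 85 or more. The second row is the affected profile. Because PH02 C.1 = N there, its corrected class is Mild whether PF04 A.4 is added to the enrolment item or replaces it.

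**Step 2: effect on the primary outcome.** Section 6.1 sets the moderate/severe variable to 0 for any determined class below Moderate. Normal and Mild both give 0, so on the plain reading the primary value for this profile is 0 before and after the correction.

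**Step 3: the other reading of Moderate.** The bullets are laid out flat, so one could read (70-84 AND GMFCS 2) OR seizure disorder OR hearing deficit. The same child then satisfies Moderate and Normal at once, and the rules contradict each other. The words that open the rule favour the plain reading.

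**Step 4: how many infants.** The SAP gives no survival rate, score distribution or follow-up seizure rate for this calculation. All four rates below are assumptions:

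affected = 168 × P(survive) × P(score 85 or more, if alive) × P(no enrolment seizure) × P(PF04 A.4 = Y)

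- Low: 168 × 0.70 × 0.50 × 0.60 × 0.03 = 1.06 (0.6% of 168)
- Middle: 168 × 0.75 × 0.55 × 0.60 × 0.05 = 2.08 (1.2%)
- High: 168 × 0.80 × 0.60 × 0.60 × 0.10 = 4.84 (2.9%)

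**Step 5: check the high case against the SAP's planning figures.** It puts 0.80 × 0.60 = 48% of randomized infants at 85 or more. Section 3.4 considers event rates of 70% and 50%, an average of 60%, which leaves 40% event-free, or 168 × 0.40 = 67.2 infants. Only event-free infants can be Normal. Even if all 67.2 scored 85 or more, the high case becomes 67.2 × 0.60 × 0.10 = 4.03. The formula also has no factor for absence of other deficits. Both points pull the figure down.

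**The case against.** The strongest objection is that PF04 A.4 records any seizure since discharge. That is broader than the seizure disorder named in Mild, and broader still than the active, treated disorder named in Moderate. A child with PF04 A.4 = Y may have had one provoked seizure, so calling that child Normal need not be wrong. This stands in part. The SAP does not show that every affected child has epilepsy, and a reader should not infer that a true disability is certainly being coded as none. The inconsistency remains, because the SAP itself uses PF04 A.4 to code a seizure disorder in Moderate and uses no follow-up seizure information at all in Mild and Normal.

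A second objection is that later seizures are not lost, since section 6.4 lists them separately with no restriction on cognitive score. That is correct: what is lost is confined to the Mild/Normal split and the outcomes built on it. Section 6.4 also presents its list as outcomes that may be considered, and the table shells for the primary paper are not at hand, so it is not established which of these outcomes will be published.

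A third objection is that this shares a root with the use of the enrolment item in Moderate, and that one consistent definition would settle both. That is fair as to the remedy. The lines affected here are different, though, and correcting Moderate alone would leave Mild and Normal as they are.

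**Conclusion.** The point holds for a specific profile: score 85 or more, no enrolment seizure, no GMFCS, vision or hearing deficit, and PF04 A.4 = Y. Such a child is classed Normal, against the wording of Mild and the stated reliance on the follow-up exam.

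Two broader conclusions are tempting and not supported. One is that every survivor scoring 85 or more with later seizures is classed Normal; with PH02 C.1 = Y the same child is Mild. The other is that the primary outcome is biased; on the plain reading of Moderate it is unchanged. It would be affected only under the alternative reading in step 3, which the wording does not favour.

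The size is probably a few infants at most. The range of about 1 to 5 of 168 rests wholly on assumed rates, and the planning figures suggest its upper end is high. The effect is on secondary disability outcomes. It is worth correcting because the rule as written gives a class that its own wording does not support, and the correction is cheap.

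**What to change.** In 6.1, use the follow-up seizure item in the seizure limb of Mild (= Y) and in the conditions for Normal (= N). Amend the two together so that no child meets both or, on this item, neither. State one follow-up definition of seizure disorder and use it in Moderate, Mild and Normal. PF04 A.4 is the item the SAP already uses. If it is judged too broad because it captures any seizure since discharge, name the narrower follow-up item and use that in all three rules.

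The cost is two lines of derivation text and the matching code, plus a change to the Moderate line to carry the common definition. No new data collection is needed if PF04 A.4 is kept. The reported no-disability rate would be slightly lower, and with PF04 A.4 a child whose only event was a single or provoked seizure would be classed Mild. The change should be made before the analysis datasets are locked under 6.5.5, so that the reclassification is not made with outcomes in view.

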6.2 Safety Outcomes

The safety outcomes that will be reported in the published primary paper are given in Table 2 of the MockTablesAppendix.docx document. A list of safety outcomes that may be considered in analysis are:

- Intra-cranial hemorrhage (ICH), up to 108 hours after baseline (*Binary, PH15: A.1, PH15TYPE*)
- cardiac arrhythmia, up to 108 hours after baseline (*Binary, PH15: A.1, PH15TYPE*)
- persistent acidosis, up to 108 hours after baseline (*Binary, PH15: A.1, PH15TYPE*)
- thrombosis, up to 108 hours after baseline (*Binary, PH15: A.1, PH15TYPE*)
- major bleeding, up to 108 hours after baseline (*Binary, PH15: A.1, PH15TYPE*)
- Perforations, ulceration or bleeding from the esophageal probe, up to 108 hours after baseline (*Binary, PH15: A.1, PH15TYPE*)
- alteration of skin integrity, up to 108 hours after baseline (*Binary, PH15: A.1, PH15TYPE*)⁵
 - Erythema
 - Scherema
 - Cyanosis
 - Subcutaneous fat necrosis (during or after the intervention)
- hypoglycemia, up to 108 hours after baseline (*Binary, PH15: A.1, PH15TYPE*)
- hyperglycemia, up to 108 hours after baseline (*Binary, PH15: A.1, PH15TYPE*)
- receipt of ECMO, up to 108 hours after baseline (*Binary, PH15: A.1, PH15TYPE*)
- PPHN, up to 108 hours after baseline, make sure this variable is only used in analysis/reports concerned with the “during intervention” time period. (*Binary, PH15: A.1, PH15TYPE*)
- thrombocytopenia, up to 108 hours after baseline (*Binary, PH15: A.1, PH15TYPE*)
- necrotizing enterocolitis, up to 108 hours after baseline (NEC as SAE) (*Binary, PH15: A.1, PH15TYPE*)
- SIP (*Binary, PH15 G.5 = ‘Y’ and date G.5.a = birthdate*)
- Other SAE
- Clinical Seizures during intervention (*Binary, PH13: D.1.b = ‘Y’*)
- Electrographic seizures (*Binary, PH13: D.2.a = ‘Y’, and date/time D.2.b within end of intervention period*)
- New ventilation requirement during 72 hr (*Binary, Use PH08 respiratory support information for 24 Hr, 48 Hr, or 72Hr time points*)

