2.2 Study Objectives

2.2.1 Study Hypotheses

The risk of death or moderate or severe disability at 18-22 months corrected age will be decreased in infants 33 0/7 - 35 6/7 wks GA and ≥ 1500 grams birth weight with moderate or severe NE due to presumed perinatal hypoxia-ischemia at < 6 hours age who undergo targeted temperature management with whole body hypothermia to 33.5°C (as monitored by esophageal temperature [Tes]) for 72 hours than in those with core temperature (also per Tes) targeted at 37.0°C (controls).

Primary objectives

- 1) To assess differences in death or moderate/severe disability at 18-22 months in enrolled infants randomized to whole body hypothermia for 72 hours, compared to those randomized to normothermia for 72 hours.
- 2) To determine short-term safety (i.e., within 108 hours of baseline [time of insertion of esophageal probe]) of targeted temperature management with whole body hypothermia for 72 hours in infants 33 0/7 -35 6/7 weeks GA with moderate or severe NE at ≤ 6 hours of age. Safety criteria will include serious adverse effects (SAEs): intracranial hemorrhage, cardiac arrhythmia; persistent acidosis;

thrombosis; bleeding; skin changes; necrotizing enterocolitis (NEC); spontaneous intestinal perforation (SIP); esophageal perforation attributable to the placement of the esophageal tube, ulceration or bleeding from the esophageal probe; hypo- and hyperglycemia; receipt of ECMO; thrombocytopenia, and death.

Secondary objectives

To assess differences between study groups with respect to a select set of secondary efficacy and safety outcomes which are listed in Sections 6.2 and 6.3.

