3.2 Study Intervention and Process

Infants were randomized within 6 hours of age to either whole body cooling or normothermia for 72 hours. The targeted temperature management for the whole body cooling group included a targeted temperature of Tes 33.5°C, (acceptable Tes 33.0 – 34.0°C); the targeted temperature management for normothermia included a targeted temperature range of Tes 36.5 – 37.3°C, with steps to prevent Tes $>37.3^{\circ}\text{C}$). In both groups the treatment period was 72 hours. Hypothermia is attained and maintained with the Cincinnati Sub-Zero Hyper/Hypothermia Device. Surveillance for safety and adverse events within 108 hours of baseline (insertion of esophageal probe) is conducted. This includes cranial ultrasound no later than 24 hours after baseline read by local center readers. All survivors undergo brain MRI after the intervention at 10-17 days of age, with strong encouragement to obtain the MRI after the intervention or prior to NICU discharge/transfer to non-NRN center (if <10 -17 days of postnatal age). MRI studies obtained at other times post-hypothermia/control intervention are included as well, and all enrolled babies undergo standard interdisciplinary neurodevelopmental assessment at 18-22 months corrected age (although the Covid pandemic occasionally required deferral of this visit, in which case the visit was scheduled as early as possible once follow-up visits were possible).

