4.2 Protocol violations/Deviations

Protocol violations (PV) and minor protocol deviations (MPD) were collected using a specified set of descriptions. Possible reasons for PV and MPD were:

- Study intervention never started
- Wrong treatment intervention applied
- Infant ineligible
- No consent
- Neuro exam not done
- Wrong stratification variables used at randomization
- Too early removal of esophageal probe
- Infant randomized after 6 hours
- Intervention initiated after 6 hours and 30 minutes
- Intervention discontinued early
- Equipment malfunction
- Cranial ultrasound completed outside of protocol-specified age window
- Tepid sponge bath not provided
- Infant not rewarmed per protocol
- Other violation

PVs and MPDs will be descriptively summarized in terms of infants per arm with any PV(MPD) and in terms of number of PV(MPD) per arm.

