6.3 Hospital Course Outcomes

Hospital Course outcomes that may be considered in analysis are:

- Proven NEC (*Binary, PH13, G.4, if PH13PNEC = 2 or 3.*)
- Spontaneous Intestinal perforation without proven NEC (SIP) (*Binary, PH13: G.5, PH13GAST, if PH13GAST = ‘Y’*)

⁵ Subcutaneous fat necrosis may occur after 108 hours.

- seizures after beginning of assigned treatment {Clinical Seizures} (Binary, PH13: D.1.b, D.1.c, D.1.d, D.1.e, taken from PH13SZAB, or PH13SZDM, or PH13SZRW, or PH13SZNT equal to 'Y')
- culture-positive bloodstream or infection of other normally sterile site at >3 days (Binary, PH13: E.1, E.2, PH13SEPT or PH13MENG needs to be 'Y')
- persistent pulmonary hypertension (PPHN) after start of intervention period (Binary, PH13: B.2, PH13PPHN)
- metabolic abnormalities after start of intervention period (Binary, PH13: I.1, I.2, I.3, I.4, I.5, I.6, I.7, PH13HYGL = 'Y' or PH13HYRG = 'Y' or PH13HYCA = 'Y' or PH13HYMA = 'Y' or PH13HYKA = 'Y' or PH13HYRK = 'Y' or PH13HYPH = 'Y')
- treatment with vasopressors and/or steroids after start of intervention period (Binary, PH13: C.7, PH13INOV)
- oliguria after start of intervention period (Binary, PH13: F.1, PH13OLIG)
- anuria after start of intervention period (Binary, PH13: F.2, PH13ANUR)
- liver dysfunction after start of intervention period (AST>200 IU and/or ALT>100 IU) (Binary, PH13: G.7, PH13EAST)
- liver dysfunction after start of intervention period (elevated direct bilirubin) (Binary, PH13: G.8, PH13EDBR)
- clinically diagnosed coagulopathy after start of intervention period (Binary, PH13: H.1, PH13DIC)
- days receiving oxygen/mechanical ventilation (Continuous, PH13: B.6, B.7, B.8, based on PH13DVEN and PH13DOXY, and PH13DCPA)
- Ventilation (Binary, if days receiving oxygen/mechanical ventilation > 0 then = yes)
- duration of NICU stay among survivors (Continuous, PH13: R.1, PH13DSDT (date of discharge) minus PH05: A.1.a, PH5BRTDT (birthdate))
- Bowel perforation (multi-level, = 'NEC' if PH13 G4 = 2, = 'NEC with Perforation' if PH13 G4 = 3, = 'SIP if PH13 G5 = 'Y')
- neurological injury by cranial ultrasound within 24 hours of enrollment, identified by local reader (Binary, PH12, see sub-section Analysis of Ultrasound, CT scan, MRI and encephalopathy outcomes under section 6.5.5.)
- Abnormal neurological examination at discharge
- Death prior to discharge

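### The SIP safety outcome counts only perforations dated on the day of birth, although the primary safety objective covers 108 hours from baseline, and the form it cites does not match section 6.3

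*SAP*

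**What the plan says.** Primary objective 2 (SAP section 2.2.1) concerns "short-term safety (i.e., within 108 hours of baseline [time of insertion of esophageal probe"], and its list of safety criteria includes SIP. Section 3.2 repeats the window: "Surveillance for safety and adverse events within 108 hours of baseline (insertion of esophageal probe) is conducted".

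Section 6.2 turns this into derivations. The 13 items from intracranial hemorrhage through necrotizing enterocolitis each carry the 108-hour limit and are read from item A.1 of form PH15. SIP comes next and is handled differently. It requires a yes at item G.5, cited on PH15, together with "date G.5.a = birthdate". No 108-hour limit is given.

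Section 6.3 lists "Spontaneous Intestinal perforation without proven NEC (SIP") again as a hospital-course outcome. There item G.5 is on form PH13, with no date condition. The multi-level bowel perforation item in 6.3 also takes G.5 from PH13. The note closing section 6.3 puts the two lists under separate reporting headings, one for the intervention period and one for birth to death or discharge.

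**The concern.** A programmer who follows section 6.2 literally would drop every SIP dated after the birth date from the intervention-period count. That includes perforations during the 72 hours of treatment and in the remaining 36 hours of the safety window (108 − 72 = 36). The rule also has no lower limit at baseline, so a perforation on the birth date but before the probe was placed would count.

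SIP is a named criterion of a primary objective. Section 6.5.5 plans a posterior probability of harm and a 95% credible interval for binary safety outcomes. If SIP is analyzed from this derivation, those summaries would describe the birth date and not the period the objective asks about. The conflicting form citation leaves it unclear which record supplies the event.

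**Working it through.** The SAP states no figure on this point, so there is none to reproduce. The check asks how much of the 108-hour window the birth-date rule can cover.

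**Inputs from the SAP**
- Window: 108 hours from probe insertion (sections 2.2.1 and 3.2).
- Randomization within 6 hours of age (section 3.2).
- "Intervention initiated after 6 hours and 30 minutes" is a listed deviation (section 4.2), so I take baseline as 0 to 6.5 hours after birth.

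**Bound that needs no assumption.** A calendar date lasts 24 hours, so coverage is at most 24/108 = 22.2%. At least 108 − 24 = 84 hours (77.8%) are excluded for every infant.

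**Average coverage, under an assumption.** Let U be the hours from birth to the next midnight and t0 the hours from birth to baseline. Covered share = max(0, U − t0)/108. The SAP gives no birth times. If U is uniform over 0 to 24:
- mean share = (24 − t0)² / (48 × 108)
- largest share = (24 − t0)/108
- proportion of infants with no coverage (baseline after midnight) = t0/24

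| t0 (hours) | Mean share | Largest share | No coverage |
|---|---|---|---|
| 0 | 576/5184 = 11.1% | 22.2% | 0% |
| 3 | 441/5184 = 8.5% | 19.4% | 12.5% |
| 6 | 324/5184 = 6.25% | 16.7% | 25% |
| 6.5 | 306.25/5184 = 5.9% | 16.2% | 27.1% |

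**In calendar dates.** 108/24 = 4.5 days, so the window touches 5 dates when baseline is before noon and 6 when it is after noon. The rule accepts one of them, or none when baseline falls after midnight.

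**Does another section restore the window?** No. The hospital-course SIP in section 6.3 is not limited to 108 hours. The residual category for other SAEs in section 6.2 is undefined and would not report the event as SIP. Where section 6.2 departs from 108 hours for subcutaneous fat necrosis, a footnote says so; SIP has no such note.

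**The case against.** The strongest reply is that this is a drafting slip of limited consequence. The line cites an apparently wrong form and applies a date test that conflicts with the heading it is reported under, so it reads as incomplete and not as a deliberate restriction. That is probably right. It makes this an inconsistency to reconcile, but the SAP supplies these references for derivation and no other section gives the intended SIP window.

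Second, SIP events are not lost to the trial. Section 6.3 counts them through discharge without a date condition, and section 6.5.5 analyzes hospital outcomes on the FAS. This stands: a perforation on a later day still enters a between-arm comparison. It does not answer the 108-hour question.

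Third, section 6.2 introduces its list as outcomes that may be considered, and the mock tables that fix the published content are not at hand. This also stands: whether this derivation reaches the primary paper cannot be checked.

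A reader might infer that the rule would report almost no SIP whatever the true rate. The document does not support that. The shares above are shares of hours, and they equal shares of events only if onset is uniform over the window, which the SAP does not say. Nor does the SAP show a direction of bias between arms, since the same rule applies to both.

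**Conclusion.** The derivation is wrong as written. It conflicts with primary objective 2, with the 108-hour window of the 13 preceding items, and with the form cited in section 6.3. It excludes at least 78% of the safety window for every infant, and that bound rests on no assumption. The mean exclusion of about 89% to 94% assumes uniform birth times and baseline at 0 to 6.5 hours after birth. The number of SIP events omitted or wrongly included cannot be stated from the document. The effect is confined to one safety item, whose events remain visible in the hospital-course outcome. It still deserves correction, because that outcome cannot stand in for the 108-hour count.

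**What to change.** In section 6.2, replace the birth-date condition for SIP with onset from baseline to 108 hours after baseline. Use date and time if both are recorded.

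The SAP describes G.5.a only as a date, whereas the electrographic seizure item in the same list uses date and time. If no time is held, state a calendar-date rule, for example from the date of baseline through the date of baseline + 108 hours. Such a rule spans 5 or 6 whole dates (120 or 144 hours), so it admits 12 or 36 hours outside the window, including any time before probe insertion on the baseline date. The SAP should acknowledge this.

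Confirm whether item G.5 sits on PH13 or PH15 and use the same reference in sections 6.2 and 6.3.

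The cost is one derivation line and a check of the case report forms, plus a sentence for the date rule if times are absent. As far as the SAP shows, no new data are needed.
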